Appendix 8. Study Procedures After Primary Completion Date (PCD) Until End of
Trial..... 182

SCHEDULE OF ACTIVITIES (PART 1, PART 2 AND J-LIC)

The schedule of activities table provides an overview of the protocol visits and procedures. Refer to the [ASSESSMENTS](#) section of the protocol for detailed information on each assessment required for compliance with the protocol.

The investigator may schedule visits (unplanned visits) in addition to those listed in the schedule of activities in order to conduct evaluations or assessments required to protect the well-being of the patient.

See [Appendix 6](#) for alternative measures during public emergencies including the COVID-19 pandemic.

Protocol Activity	Screening	Active Treatment Phase [†] - One Cycle = 28 days					End of Treatment/ Withdrawal [§]	Post-Treatment Follow-Up [*]
		Cycles 1 and 2			Cycles ≥3			
Study Day	Within 28 days prior to registration unless specified otherwise	Day 1 [‡]	Day 8	Day 15	Day 21	Day 1		
Visit Window				±3 days	±3 days	±3 days	±5 days	
Informed Consent ¹	X							
Medical/Oncological History ²	X							
Baseline Signs/Symptoms ³		X						
Physical Examination ⁴	X						X	
Abbreviated Physical Examination ⁵		X	X	X	X	X		X
Vital Signs ⁶	X	X	X	X	X	X	X	X
Contraception Check ⁷	X	X				X	X	
ECOG Performance Status ⁸	X	X				X	X	X
12-Lead ECG ⁹	X	X	X C1 ⁹ and C2 ⁹	X C1 only		X	X	
Laboratory Studies¹⁰								
Hematology	X	X	X	X	X	X	X	(X)
Blood Chemistry	X	X	X ¹¹	X ¹¹	X ¹¹	X	X	(X)
Coagulation	X	X						(X)
Urinalysis	X						X	(X)
Pregnancy test	X	X				X	X	
Viral disease screening ¹²	X							
Disease Assessment								
Tumor markers (for breast cancer: CA 15-3 and CEA; Part 1 only for ovarian cancer: CA 125)	X	X				X	X	
CT/MRI Scans of Chest, Abdomen, Pelvis, any clinically indicated sites of	X	Performed every 8 weeks from C1D1 (±7 days) for the first 6 months, and then every 12 weeks (±7 days)					X ¹³	

Protocol Activity	Screening	Active Treatment Phase [†] - One Cycle = 28 days					End of Treatment/ Withdrawal [§]	Post-Treatment Follow-Up [*]
		Cycles 1 and 2				Cycles ≥3		
Study Day	Within 28 days prior to registration unless specified otherwise	Day 1 [‡]	Day 8	Day 15	Day 21	Day 1		
Visit Window			±3 days	±3 days	±3 days	±5 days		±7 days
disease, and of bone lesions; Clinical evaluation of superficial disease ¹³ Follow up for Overall Survival (OS)		thereafter for up to 2 years. After 2 years, performed every 4 months thereafter.						
Study Treatment								

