For patients enrolled in dose level 1 and 2 that undergo intra patient dose escalation ([Section 3.1.5](#)), triplicate ECGs should be performed on Day 8 (within 30 min prior to the morning dose of PF-06873600) and Day 15 (within 30 min prior to the morning dose of PF-06873600 and 1 hour after the morning dose of PF-06873600) in the first cycle at the escalated dose of PF-06873600 and then on Day 1 (within 30 min prior to the morning dose of PF-06873600) of each subsequent cycle.

10. **Laboratory Studies:** Screening labs to be performed within 7 days of C1D1. Laboratory assessments can be performed earlier but will have to be repeated to be done within 7 days of C1D1. For subsequent cycles, pre-dose labs may also be drawn up to 3 days (-3 days/72 hours) in advance of scheduled dosing in order to obtain results prior to visit.

- See [Table 4](#) in [Section 7.1.3](#) for a full list of safety laboratory assessments.
- For Urinalysis, dipstick is acceptable but microscopic analyses is required if dipstick abnormal. Additional tests may be performed as clinically indicated.
- Pregnancy test at screening and Day 1 of every other cycle only for women of childbearing potential. Test may be repeated as per request of institutional review board/independent ethics committee (IRB/IECs) or if required by local regulations. See [Section 7.1.1](#).

11. **Cycle 1 and Cycle 2, Day 8, 15 and 21:** Not required for patients in Part 2.

12. **Viral disease screening tests:** Hepatitis B virus surface antigen (HBsAg), hepatitis B core antibody (anti-HBc), (HbcAb), hepatitis B surface antibody (anti-HBs), hepatitis C virus antibodies (HCVAb), human immunodeficiency virus testing (HIV), and COVID-19 to be conducted by local laboratory where required by local regulations or if warranted by patient history. For Japan only, participants with HBsAb and HbcAb should be monitored with HBV viral load (refer to [Appendix 7](#)).

Protocol Activity	Screening	Active Treatment Phase [†] - One Cycle = 28 days				End of Treatment/ Withdrawal [§]	Post-Treatment Follow-Up [*]
		Cycles 1 and 2		Cycles ≥3			
Study Day	Within 28 days prior to registration unless specified otherwise	Day 1 [‡]	Day 8	Day 15	Day 21	Day 1	
Visit Window			±3 days	±3 days	±3 days	±5 days	

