Part 1A will estimate the maximum tolerated dose/recommended Phase 2 dose/recommended dose for expansion (MTD/RDE) in sequential dose escalation safety cohorts for PF-06873600 as a single agent in women of any menopausal status and men with HR-positive HER2-negative advanced or mBC (third or fourth line setting) and in women/men with locally recurrent/advanced or metastatic TNBC and women with advanced platinum resistant ovarian cancer.

Any given PF-06873600 dose in Part 1A (or Part 1C) may be escalated or de-escalated at full or intermediate dose levels, depending on emerging clinical data. Parallel biomarker cohorts may be initiated for HR-positive HER2-negative advanced or mBC patients only, once the respective preceding dose escalation safety cohort has cleared (see [Section 3.1.1](#)).

After the MTD/RDE for PF-06873600 as a single agent has been identified in Part 1A (or Part 1C) based on safety and clinical observations, initiation of combination dose de-escalation with PF-06873600 in combination with letrozole and PF-06873600 in combination with fulvestrant independently (Part 1B) will be initiated at the single agent MTD or RDE in women of any menopausal status with HR-positive HER2-negative advanced or mBC. In Part 1B, the PF-06873600 dose can be de-escalated at full or intermediate dose levels. In addition both available formulations of PF-06873600 at the respective RDE will be studied in combination with endocrine therapy in Part 1B. Approximately 12 patients will be dosed in the respective endocrine therapy combinations, with approximately 6 patients receiving PF-06873600 IR + endocrine therapy and approximately 6 patients receiving PF-06873600 MR + endocrine therapy in both the fulvestrant and letrozole arms.

Part 2 will evaluate the dose selected (RDE) in combination with endocrine therapy (letrozole and fulvestrant in independent dose expansion arms) depending on clinical observations from Part 1B (See [Section 3.2](#)).

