9.2.2. Statistical Method for Estimating the MTD

This study contains dose escalation and/or de-escalation with single agent in Part 1 followed by a single agent and combination dose expansion (Part 2). The MTD determination will be assessed independently for each dosing regimen evaluated in Part 1A and 1C and dose de-escalation Part 1B based on the mTPI method described in [Section 9.2.1](#). The overall study design is depicted in [Figure 8](#).

Parts 1A and 1C will estimate the MTD/RDE in sequential dose escalation cohorts in:

- HR-positive HER2-negative advanced or mBC patients with prior CDK4/6 inhibitor and endocrine therapy in the advanced or metastatic setting, or
- Locally recurrent/advanced or metastatic TNBC, or
- Advanced platinum resistant epithelial ovarian cancer/fallopian tube cancer/primary peritoneal cancer.

During Part 1 dose finding, all available safety information from safety and biomarker cohorts in Part 1A and 1C will be used to determine the respective MTD/RDE. Because these additional patients in biomarker cohorts will receive a dose lower than the concurrent dose escalation safety cohort or will be enrolled at a dose following the DLT evaluation period in the first 2-4 dose escalation safety cohort patients enrolled, their potential DLT observations may not be strictly used in the mTPI method for the ongoing dose finding in Part 1A and 1C. However, the safety profile from these additional patients in biomarker cohorts will be used to establish the respective MTD or RDE in Part 1A and Part 1C, if applicable.

Part 1B will include PF-06873600 in combination with letrozole and in combination with fulvestrant. The starting dose for this combination will start with PF-06873600 at MTD/RDE for the single agent (established in Part 1A or Part 1C) and the prescribed dose for letrozole and fulvestrant, respectively. The PF-06873600 dose may be decreased if determined to be intolerable in a dose de-escalation manner based on mTPI. The MTD/RDE for this combination regimen, if selected, will be based on 6 to 12 patients.

For data analysis purpose, data from all patients receiving the MTD/RDE in Part 1B and Part 2 expansion cohort will be combined under the same treatment regimen and same tumor type.

Part 2 will evaluate the PF-06873600 dose selected (MTD/RDE) from Part 1 as a single agent (from Part 1A or Part 1C) and in combination with endocrine therapy (from Part 1B).

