9.6. Safety Analysis

Summaries and analyses of safety parameters will include all patients in the Safety Analysis Set.

9.6.1. Analysis of the Primary Endpoint for Part 1

DLT is the primary endpoint of the Pali 1 component of the study. The occurrence of DLTs observed in the dose levels to be evaluated is used to estimate the MTD as described in the [STUDY DESIGN](#) section. Adverse Events constituting DLTs will be listed per dose level.

9.6.2. Analysis of Primary Endpoints for Safety for Part 1 and 2

Adverse Events

AEs will be graded by the investigator according to the CTCAE version 4.03 and coded using the Medical Dictionary for Regulatory Activities (MedDRA). The focus of AE summaries will be on Treatment Emergent Adverse Events, those with initial onset or increasing in severity after the first dose of study treatment. The number and percentage of patients who experienced any AE, SAE, treatment related AE, and treatment related SAE will be summarized according to worst toxicity grades. The summaries will present AEs both on the entire study period and by cycle (Cycle 1 and Cycles beyond 1).

Laboratory Test Abnormalities

The number and percentage of patients who experienced laboratory test abnormalities will be summarized according to worst toxicity grade observed for each laboratory assay. The analyses will summarize laboratory tests both on the entire study period and by cycle (Cycle 1 and Cycles beyond 1). Shift tables will be provided to examine the distribution of laboratory toxicities.

For laboratory tests without CTCAE grade definitions, results will be categorized as normal, abnormal, or not done.

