7.2.5. Laboratory Data

Screening labs to be performed within 7 days of CJD1. Laboratory assessments can be performed earlier but will have to be repeated to be done within 7 days of CJD]. For subsequent cycles, pre-dose labs may also be drawn up to 3 days (-3 days/72 hours) in advance of scheduled dosing in order to obtain results prior to visit.

The laboratory results will be graded according to the NCI CTCAE v4.03 severity grade. For labs for which an NCI CTCAE v4.03 scale does not exist, the frequency of patients with values below, within, and above the normal ranges will be summarized by dose. Baseline evaluations for laboratory data are those collected:

- Within 28 days prior to Cycle 1/Day 1.
- Closest but prior to Cycle 1/Day 1 if there is more than one baseline evaluation.

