9.2.3.2. Laboratory Tests Abnormalities

The number and percentage of patients who experienced laboratory test abnormalities will be summarized according to worst toxicity grade observed for each laboratory test. The analyses will summarize laboratory tests based on the entire study period (all cycles). Shift tables will be provided to examine the distribution of laboratory abnormalities, and worst on-study abnormalities will be summarized. The Safety Analysis Set will be used.

For laboratory tests without CTC grade definitions, results will be categorized as normal, abnormal high/low or not done.

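### A pooled chemistry-abnormality rate would mix Part 1B patients (8 scheduled post-dose draws through C3D1) with Part 2 patients (2), and the SAP has no split by part

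*SAP*

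**What the plan says.** **Schedule.** In the Schedule of Activities for Part 1, Part 2 and J-LIC, the "Blood Chemistry" row is marked on Days 8, 15 and 21 of Cycles 1 and 2, each time with footnote 11. The hematology row carries no such footnote. Footnote 11 reads "Not required for patients in Part 2". From Cycle 3 both parts have chemistry on Day 1 of each cycle, and both have it at end of treatment.

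**Pooling.** Protocol 9.2.2 states that "data from all patients receiving the MTD/RDE in Part 1B and Part 2 expansion cohort will be combined under the same treatment regimen", provided the tumor type is also the same. It makes no exception for laboratory data. The SAP, which describes itself as a supplement to the protocol, neither repeats nor withdraws this rule.

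**Laboratory analysis.** SAP 9.2.3.2 states: "The number and percentage of patients who experienced laboratory test abnormalities will be summarized according to worst toxicity grade observed for each laboratory test". On the period it says "The analyses will summarize laboratory tests based on the entire study period (all cycles"), in the Safety Analysis Set. For tests without a CTCAE scale, SAP 7.2.5 says "the frequency of patients with values below, within, and above the normal ranges will be summarized by dose", so the grouping is by dose and not by part. Protocol 9.6.2 asks for more: "The analyses will summarize laboratory tests both on the entire study period and by cycle (Cycle 1 and Cycles beyond 1)". The SAP does not carry over that cycle split.

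**The concern.** A worst-observed-grade count depends on how often one looks. Two groups with the same true rate of short-lived chemistry abnormalities will show different percentages if one is sampled about weekly for 8 weeks and the other every 4 weeks. If they are then combined, the percentage describes neither schedule, and it shifts with the ratio of Part 1B to Part 2 patients.

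Laboratory abnormalities by type, frequency, severity and timing are a primary endpoint in both parts (Protocol section 2). The chemistry panel in Protocol Table 4 includes ALT, AST, bilirubin, creatinine, amylase and lipase. A reader who sets the Part 2 or pooled rate beside the Part 1 rate could credit to the treatment a difference that comes from sampling.

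**Working it through.** The documents state no laboratory rate to reproduce, so the check is a count of draws followed by an illustration.

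**1. Scheduled post-dose chemistry draws through C3D1** (Schedule of Activities, footnote 11; C1D1 is pre-dose)

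- Part 1B: Days 8, 15, 21, 29, 36, 43, 49, 57 = 8 draws.
- Part 2: Days 29 and 57 = 2 draws.
- Strictly between C1D1 and C2D1: 3 against 0.

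**2. Make-up of the pool.** Protocol 3.1 says "Approximately 12 patients will be dosed in the respective endocrine therapy combinations", about 6 per formulation. Protocol 3.2 gives about 40 patients in Arm A (fulvestrant), 30 in Arm B (letrozole) and 30 in Arm C (fulvestrant); 40 + 30 + 30 = 100, the stated Part 2 total. The share of the pool on the sparse schedule is:

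- Fulvestrant with Arm A: 40/52 = 77%, or 40/46 = 87% if only one formulation is pooled.
- Letrozole with Arm B: 30/42 = 71%, or 30/36 = 83%.
- Fulvestrant with Arms A and C: 70/82 = 85%.

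**3. Chance that a scheduled draw catches an episode.** Assumptions: one episode of fixed length L days, onset uniform over the window, no unscheduled tests. A draw on day d catches onsets in the L days ending on d. Detection is the number of window days so covered, divided by the window length.

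*Onset in the first 8 weeks (56 days).* For L = 7, Part 1B leaves two one-day gaps (between Days 21 and 22, and between Days 49 and 50), giving (56 − 2)/56 = 54/56 = 96%. Part 2 gives 2 × 7/56 = 25%.

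| Episode length | Part 1B | Part 2 |
|---|---|---|
| 3 days | 24/56 = 43% | 6/56 = 11% |
| 7 days | 54/56 = 96% | 14/56 = 25% |
| 14 days | 100% | 28/56 = 50% |
| 21 days | 100% | 42/56 = 75% |
| 28 days | 100% | 100% |

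*Onset over 6 cycles (168 days).* The SAP table covers all cycles, and Protocol 3.1 expects about 6 to 8 cycles per patient. Cycles 3 to 6 add the same four Day 1 draws to both parts (Days 85, 113, 141, 169).

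- 7 days: Part 1B (54 + 4 × 7)/168 = 82/168 = 49%; Part 2 6 × 7/168 = 25%.
- 14 days: Part 1B (56 + 4 × 14)/168 = 112/168 = 67%; Part 2 6 × 14/168 = 50%.

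Over 8 cycles (224 days), the Part 1B figures fall to (54 + 42)/224 = 43% and (56 + 84)/224 = 63%. Part 2 stays at 25% and 50%.

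**4. Pooled detection**, (n₁p₁ + 40p₂)/(n₁ + 40), for 7-day episodes in Arm A plus n₁ Part 1B patients

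- First 8 weeks: n₁ = 6, (6 × 0.964 + 10)/46 = 34%; n₁ = 12, (12 × 0.964 + 10)/52 = 41%.
- Six cycles: n₁ = 6, (6 × 0.488 + 10)/46 = 28.1%; n₁ = 12, (12 × 0.488 + 10)/52 = 30.5%.

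**5. On the scale of the table.** With an assumed true incidence of 20% and 7-day episodes starting in the first 8 weeks, the observed rate would be 19.3% in Part 1B, 5.0% in Part 2 and 8.3% in the 12 + 40 fulvestrant pool. With onset over 6 cycles, the three become 0.20 × 0.488 = 9.8%, 5.0% and 0.20 × 0.305 = 6.1%.

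**The case against.** Several points on the other side stand.

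- **Part 2 is not blind between Day 1 visits.** A reader might infer that nothing could be seen, or that the Part 2 Cycle 1 chemistry rate is zero by design. The documents do not support that. Part 2 patients still attend on Days 8, 15 and 21 for examination and hematology. Unscheduled tests are allowed, and footnote 10 lets the C2D1 sample be drawn up to 3 days early, which falls inside Cycle 1. The accurate statement is that no chemistry was scheduled in those weeks. Unscheduled tests are, however, likely to follow symptoms or known toxicity, so silent abnormalities are the ones most likely to be missed.
- **96% against 25% is not the gap in the SAP table.** It places every onset in the only window where the schedules differ. Over 6 cycles the 7-day gap is 49% against 25%. The documents give no onset pattern, so both are illustrations, and long-lasting abnormalities show no gap.
- **Pooling does not cause the Part 2 shortfall.** Pooled detection is higher than in Part 2 alone. Splitting the table makes each rate interpretable but leaves the shortfall in place.
- **The reach of the pooling rule is open.** It stands in a section on MTD estimation and covers only Part 1B patients at the MTD/RDE with the same regimen and tumor type. Its wording is general to data analysis, though, and nothing in the SAP limits it.
- **No formal contrast is planned.** The study is non-randomized and has no hypotheses (SAP 4.1), and no laboratory comparison of combination with single agent is specified. The risk is misreading of descriptive tables, not a wrong test result.

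**Conclusion.** The point holds as a limited, inexpensive improvement. The chemistry schedules differ in Cycles 1 and 2 (8 against 2 scheduled post-dose draws through C3D1) and coincide from Cycle 3. The protocol combines the two groups, and the SAP gives one worst-grade count over all cycles with no split by part and no rule for unequal sampling. A pooled chemistry rate therefore mixes unequal ascertainment, with 71% to 87% of the pool on the sparser schedule.

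The direction is clear: short early abnormalities are under-counted in Part 2 relative to Part 1B. The size is not known. It depends on onset, duration and the amount of unscheduled testing, none of which the documents give. On scheduled draws alone, the 7-day gap runs from 96% against 25% (all onsets in the first 8 weeks) to 43% against 25% (onsets over 8 cycles), and it closes at 28 days. Hematology is not affected. A reader might go further and conclude that the Part 2 chemistry results are uninformative, or that a combination will wrongly appear safer than the single agent. The documents establish neither.

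**What to change.** In SAP 9.2.3.2:

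- Tabulate chemistry worst grade and shifts separately for Part 1B and Part 2, keeping every observed value in each, including unscheduled ones. Apply the same split to the ungraded tests in SAP 7.2.5.
- State the two chemistry schedules in a footnote to these tables.
- If a pooled or cross-part chemistry rate is shown, add a supplementary version limited to the common scheduled visits (Day 1 of each cycle and end of treatment). It should not replace the full table, because it would drop observed Part 1B Day 8, 15 and 21 values and unscheduled values, some possibly high grade.
- If the by-cycle summary in Protocol 9.6.2 is produced, use as the Cycle 1 denominator the patients with at least one post-baseline chemistry value in Cycle 1.
- Hematology may stay pooled.

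The cost is SAP wording, one table split and possibly one supplementary table, with no new samples and no change to the visit schedule. Each chemistry table will have fewer patients, and detection in Part 2 itself is not improved.

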9.2.3.3. Vital Signs

Vital signs data will be presented as summaries for change from baseline and as categorical summaries for absolute value, decrease and increase from baseline. The Safety Analysis Set will be used.

9.2.3.4. Electrocardiogram

The analysis of ECG results will be based on patients in the safety analysis set with baseline and on-treatment ECG data.

ECG measurements (an average of the triplicate measurements) will be used for the statistical analysis and all data presentations. Any data obtained from ECGs repeated for safety reasons after the nominal time-points will not be averaged along with the preceding triplicates. Interval measurements from repeated ECGs will be included in the outlier analysis (categorical analysis) as individual values obtained at unscheduled time points.

QT intervals will be corrected for heart rate (QTc) using standard correction factors (ie, Fridericia's and possibly a study specific factor). Data will be summarized and listed for QT, HR, RR, PR, QRS, QTcF and QTcB by treatment and dose. Individual QTc (QTcF and QTcB) intervals will be listed by compound, time and dose. Descriptive statistics (n, mean, median, standard deviation, minimum, and maximum) will be used to summarize the absolute QTcF value and changes from baseline in QTcF after treatment by compound, dose and by time point. For each patient and by treatment, the maximum change from baseline

will be calculated as well as the maximum post-baseline value across time-points. Categorical outlier analysis of the QTcF data will be conducted and summarized as follows:

- The number of patients with maximum change from baseline in $30\text{ms} < \text{QTcF} \leq 60\text{ms}$, $\text{QTcF} > 60\text{ms}$.
- The number of patients with maximum post-dose (post-baseline) $450\text{ms} < \text{QTcF} \leq 480\text{ms}$, $481 < \text{QTcF} \leq 500\text{ms}$ and $\text{QTcF} > 501\text{ms}$.

In addition, the number of patients with detected and undetected QT values $> 501\text{ msec}$ will be summarized.

Shift tables will be provided for baseline vs worst on treatment corrected QT (one or more correction methods will be used) using maximum CTCAE (version 4.03) Grade. Shift tables will also be provided for ECG abnormality at baseline vs on treatment (yes, no, not done: (n, %)). Patients experiencing clinically relevant morphological ECG changes will be summarized (including frequency and percentage).

If more than one ECG is collected at a nominal time post dose (for example, triplicate ECGs), the mean of the replicate measurements will be used to represent a single observation at that time point. If any of the three individual ECG tracings has a QTcF value $> 501\text{ msec}$, but the mean of the triplicates is $\leq 501\text{ msec}$, the data from the subject's individual tracing will be described in a safety section of the study report in order to place the $> 501\text{ msec}$ value in appropriate clinical context. However, values from individual tracings within triplicate measurements that are $\leq 500\text{ msec}$ will not be included in the categorical analysis unless the average from those triplicate measurements is also $\leq 500\text{ msec}$. Changes from baseline will be defined as the change between QTcF post dose from Day 0, or the pre-dose values on Day 1.

The effect of drug concentrations on QTcF change from baseline will be explored graphically. In addition, an attempt will be made to explore and characterize the relationship between plasma concentration and QTcF interval length using a PK/PD modeling approach. If a PK/PD relationship is found, the impact of subject factors (covariates) on the relationship will be examined.

Patients experiencing clinically-relevant morphological ECG changes will be summarized (including frequency and percentage).

Changes from baseline for the ECG parameters QT interval, heart rate (HR), QTc interval, PR interval and QRS interval will be summarized by cohort and timepoint. Categorical data analysis will follow [Appendix 1](#).

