7.1.4. Vital Signs and Physical Examination

Patients will have a full physical examination to include an examination of all major body systems and breasts, height (at screening only), weight, blood pressure and pulse rate, which may be performed by a physician, registered nurse or other qualified health care provider, as acceptable according to local regulation. Blood pressure and heart rate should be recorded after approximately 5 minutes rest. An abbreviated physical exam is an assessment for emergent toxicities or changes from prior visits and a symptom directed exam conducted by a physician, trained physician's assistant or nurse practitioner, as acceptable according to local regulation.

7.1.5. (12-Lead) Electrocardiogram

Standard electrocardiogram (ECG): 12-lead (with a 10-second rhythm strip) tracing will be used for all ECGs. It is preferable that the machine used has a capacity to calculate the standard intervals automatically. At each time point (see the Schedule of Activities), 3 consecutive ECGs (except single ECG at screening and End of Treatment) will be performed at approximately 2 minutes apart to determine the mean QTcF interval. If the mean QTcF is prolonged ≥ 501 msec, ie, CTCAE Grade ≥ 3), then the ECGs should be re-evaluated by a qualified person at the site for confirmation as soon as the finding is made, including verification that the machine reading is accurate.

If manual reading verifies a QTcF of ≥ 501 msec, immediate correction for reversible causes (including electrolyte abnormalities, hypoxia and concomitant medications for drugs with the potential to prolong the QTcF interval) should be performed. In addition, repeat ECGs should be immediately performed hourly for at least 3 hours until the QTcF interval falls below 501 msec. If QTcF interval reverts to less than 501 msec, and in the judgment of the investigator(s) and sponsor is determined to be due to cause(s) other than investigational product, treatment may be continued with regular ECG monitoring.

If reversible causes are treated and the QTcF intervals remains ≥ 501 msec, the investigational product will be held until the QTcF interval decreases to less than 501 msec. Patients will then restart the investigational product at the next lowest dose level.

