7.2.7. ECG and QTc Interval

Standard electrocardiogram (ECG): 12-lead (with a 10-second rhythm strip) tracing will be used for all ECGs. It is preferable that the machine used has a capacity to calculate the standard intervals automatically. At each time point (see the Schedule of Activities in the Protocol), 3 consecutive ECGs (except single ECG at screening and End of Treatment) will be performed at approximately 2 minutes apart to determine the mean QTcF interval. If the mean QTcF is prolonged ≥ 501 msec, ie, CTCAE Grade ≥ 3 , then the ECGs should be re-evaluated by a qualified person at the site for confirmation as soon as the finding is made, including verification that the machine reading is accurate.

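### The SAP's QTcF outlier classes leave 1 ms holes at 480–481 and 500–501 ms, so an unrounded triplicate mean can fall in no class

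*SAP*

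**What the plan says.** Protocol Section 2 and SAP 2.3 list heart-rate-corrected QT (eg, QTcF) among the primary endpoints for Part 1 and again for Part 2.

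SAP 9.2.3.4 (Electrocardiogram) tabulates "The number of patients with maximum post-dose (post-baseline") QTcF in three classes. As printed, these are above 450 up to and including 480 ms, above 481 up to and including 500 ms, and above 501 ms. It adds a separate count of patients with QT values above 501 ms. SAP Appendix 1 repeats the limits 450, 480, 481, 500 and 501, with every sign printed as strict.

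On the unit of analysis, the same section says "ECG measurements (an average of the triplicate measurements) will be used for the statistical analysis and all data presentations". For replicate tracings at one nominal time, "the mean of the replicate measurements will be used to represent a single observation at that time point". Repeat ECGs taken for safety reasons enter the outlier analysis as individual values. Nothing is said about rounding.

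On the threshold, SAP 7.2.7 asks for re-evaluation as follows: "If the mean QTcF is prolonged ≥ 501 msec". Protocol 7.1.5 has the same value: "If manual reading verifies a QTcF of ≥ 501 msec, immediate correction for reversible causes". It then calls for hourly repeat ECGs "until the QTcF interval falls below 501 msec".

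The SAP rule for single tracings within a triplicate (end of 9.2.3.4) uses 501 ms to decide which tracings are described in the report and 500 ms to decide which enter the categorical analysis.

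**The concern.** Classes of this kind should cover every possible value above their lower limit. Here the upper limit of one class and the lower limit of the next are different numbers, 480 then 481 and 500 then 501. That works only for whole-millisecond data. A mean of three tracings is usually not a whole number.

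Each patient is counted once, by the maximum. A patient whose maximum falls in a hole does not move to the class below but disappears from the table. A maximum of 500.67 ms would then be reported less prominently than one of 490 ms. The upper hole lies just below the value at which the protocol starts re-evaluation, which is where a reader of a QTcF table looks first.

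**Working it through.** No sample size, power or error rate is involved. The check is whether the classes cover the values they are applied to.

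**Inputs.** The class limits come from SAP 9.2.3.4 and Appendix 1. The analysed value is the triplicate mean (SAP 9.2.3.4). Assumption: single tracings are recorded in whole milliseconds, so means move in steps of 1/3 ms. The documents do not state the recording precision.

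**Hand examples.**
- Readings 480, 480, 481: mean = 1441/3 = 480.33 ms. This is above 480 and below 481, so it has no class.
- Readings 500, 501, 501: mean = 1502/3 = 500.67 ms. This is above 500 and below 501, so it has no class.

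**Full check.** Every multiple of 1/3 ms from 451 to 520 ms was tested under three readings of the signs and under two contiguous sets of classes.

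| Classes | Values in no class (ms) |
|---|---|
| SAP 9.2.3.4 as printed | 480.33, 480.67, 481, 500.33, 500.67, 501 |
| SAP Appendix 1 as printed (all strict) | 480, 480.33, 480.67, 481, 500, 500.33, 500.67, 501 |
| Same limits, every sign inclusive | 480.33, 480.67, 500.33, 500.67 |
| >450 to ≤480, >480 to <501, ≥501 | none |
| >450 to ≤480, >480 to ≤500, >500 | none |

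No value falls in two classes under any row.

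**What does and does not depend on the signs.** The four non-integer values are lost in each of the first three rows, because the limits themselves are 1 ms apart. The whole-number values 480, 481, 500 and 501 are lost only under particular readings of the signs.

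**Exactly 501 ms.** The protocol side is clear without any sign: the wording of 7.1.5 requires the interval to fall below 501, so 501 itself counts as prolonged. The SAP side turns on whether its sign at 501 is strict. If it is, a patient at exactly 501 ms is in neither the top class nor the additional count.

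**How often means are non-integer.** If the remainders of the readings on division by 3 are roughly uniform, the sum of three whole numbers is divisible by 3 in about 1/3 of cases. About 1 − 1/3 = 2/3 of triplicate means are then non-integer. This shows that such values are ordinary. It does not say how many patients have a maximum inside one of two 1 ms windows, and the documents give no QTcF distribution from which to estimate that.

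**The case against.** **The signs cannot be trusted.** Several operators in this part of the SAP are visibly damaged. Appendix 1 prints strict signs where 9.2.3.4 prints inclusive ones for the same classes, and the sentence on single tracings makes sense only if its signs were misread. A lost ≥ at 501 is therefore plausible, all the more because SAP 7.2.7 prints ≥ 501. Against this, 501 is printed with a strict sign in several places, and the single-tracing rule pairs a tracing above 501 with a mean at or below 501, which fits a strict reading. The text does not settle it. A reader might infer that a value of exactly 501 ms, and every maximum from just above 480 through 481 or from just above 500 through 501, is certainly dropped. The documents do not support that: the end points depend on the signs, and only the open intervals are lost under every reading.

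**The gap vanishes if values are rounded.** With whole milliseconds and inclusive limits, 480/481 and 500/501 are adjacent. That is true, and it may be what was intended, but no rounding rule is stated. Rounding alone would not suffice under the signs printed in 9.2.3.4, because 481 and 501 would still be unclassified. Not every value is a triplicate mean either: the end-of-treatment ECG and repeat safety ECGs are analysed singly.

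**The patients are not lost to view.** This stands. Individual QTc listings, descriptive maxima and a shift table by worst CTCAE grade are all planned, and Protocol 7.1.5 and SAP 7.2.7 equate 501 ms or more with Grade 3 or higher. A patient at 501 would appear in that shift table, although the two tables would disagree if the outlier sign is strict.

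**Nothing is decided from these counts.** This also stands. SAP 4.1 and 9.1 plan no hypothesis tests. A reader might infer that a patient in a gap would miss the required re-evaluation; the documents do not support that, because action at the site follows Protocol 7.1.5 and not this table.

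**Conclusion.** The point holds. Under any reading of the signs, a maximum strictly between 480 and 481 ms or strictly between 500 and 501 ms is counted in no QTcF class, because triplicate means are analysed without a rounding rule. The loss of exactly 501 ms from the top class and the additional count is conditional on the printed sign being strict.

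The size is small. Few patients can have their maximum in two 1 ms windows, and the two-thirds figure must not be read as a share of patients. The analysis is descriptive, and the listings and shift table still show the values. It is nevertheless worth correcting: this is the outlier table for a listed primary safety endpoint, one gap sits next to the documents' own threshold, and the single-tracing rule uses both 500 and 501.

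The conclusion rests on means being left unrounded, about which the SAP is silent. The 1/3 ms steps in the check rest on whole-millisecond readings, but finer readings would leave the same holes.

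**What to change.** Make the classes contiguous in both SAP 9.2.3.4 and SAP Appendix 1, with the same signs in each. Either of these works:

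- >450 to ≤480, >480 to <501, and ≥501 ms. This uses the value already in Protocol 7.1.5 and SAP 7.2.7 and keeps the top class in line with the documents' Grade 3 limit in the shift table.
- >450 to ≤480, >480 to ≤500, and >500 ms, with a separate count of ≥501 ms. Without that count, a value such as 500.33 would sit in the top class while falling below the documents' Grade 3 limit.

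Then use one consistent limit for the additional count and for the single-tracing rule at the end of SAP 9.2.3.4.

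The cost is SAP and table-shell wording, plus the matching change in the table program. No data collection, protocol threshold or clinical action changes.
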